## 9.12 Early Withdrawal (Phase 2)

Any subject may withdraw early from the study at any time for any reason. Upon withdrawal, assessments will be performed following Table 2: Schedule of Assessments for Phase 1 and Phase 2. The investigator may also terminate a subject's participation in the study if it is in the best interest of the subject or if the Sponsor or local regulatory agency (e.g., FDA) terminates the study.

The Early Withdrawal visit will include:

- A1C (blood draw sent to NGSP laboratory)
- Review of concomitant medications
- Height
- Weight
- Assessment of vital signs
- Assessment of AEs since last visit
- Completion of questionnaires (see Table 4: Questionnaires for specific requirements by age group):
  - WHO-5
  - EQ-5D
  - T1DDS
  - DTSQc
  - Hypoglycemia Confidence Scale
  - HABS
  - PSQI
  - IDSS (T1)
  - SUS
  - PAID-(Teen, Child)
  - INSPIRE-(Adult, Youth, Parent)
    - Used to measure a caregiver's experience of the support they receive
  - Human Factors (HF) Questionnaire
    - Measures trust in the Horizon System
  - Clarke Questionnaire
- Discontinuation of Horizon Data Portal monitoring
- Return all study devices

- Complaints/device deficiencies such as occlusion alarms and system hazard alarms since last visit
- Device uploads for BG and ketone meter
- Data review by clinician

The reason for withdrawal will be recorded, and their participation in the study will end.

In the event of a subject's death during the study, the subject's participation will be considered terminated and the date of death will be used as the date of study exit.

## 10 HYBRID CLOSED-LOOP – PHASE 3

The hybrid closed-loop Phase 3 extension will commence at **Visit 13** upon conclusion of hybrid closed-loop Phase 2 and after all assessments are performed according to Table 2: Schedule of Assessments for Phase 1 and Phase 2. Phase 3 assessments are to be performed according to Table 3: Schedule of Assessments for Phase 3.

For subjects that do not extend their participation into the extension phase, the reason for study exit at Visit 13 will be documented. This will not be considered an early withdrawal from the study.

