Subjects extending their participation into the extension phase are to be consented for both the first 6-month and the second 6-month interval of Phase 3. Consent for each interval must occur on or any time before commencing that study interval (e.g. consent for first 6-months of Phase 3 must occur on or before Visit 13, consent for second 6-months of Phase 3 must occur on or before Visit 19).

During the hybrid-closed loop extension phase, subjects will continue to perform the following:

- Adjust pump and CGM parameters to optimize their insulin therapy in collaboration with the recommendations from the clinical study staff
- Follow their pre-exercise management such as insulin reduction for meal boluses, consumption of snacks, or adjusting their insulin delivery settings
- Treat themselves per their usual routine if they become hypoglycemic or hyperglycemic or have symptoms of either at any time during the study
- Consume meals and snacks of their own choosing. Subjects will be encouraged to estimate the grams of carbohydrates for each meal or snack per their usual routine. The estimate should be entered into the meal bolus calculator.
- Administer meal boluses per their usual dosing routine
- Participate in challenge visits as specified
- Change their CGM per manufacturer's instructions or sooner if necessary
- Change the Pod at least once every 72 hours

Subjects will have scheduled follow-up visits. Visits will be conducted either in person at the clinical study site or over the telephone. Subjects may also choose to use email or text as a substitute for their scheduled telephone visit.

The duration of the hybrid closed-loop extension phase will last approximately 12-months.

Subjects will be encouraged to call the clinical study site at any time with any concerns.

### 10.1 Visit 14

**Visit 14** will be conducted either over the telephone or in person at the clinical study site on Study Day 120 ± 5 days. This visit will include:

- Review of concomitant medications
- Assessment of adverse events since previous visit
- Complaints/device deficiencies such as occlusion alarms and system hazard alarms since last visit
- Device uploads for BG and ketone meter (if visit is conducted at the clinical site)
- Data review of Automated Mode use by clinician

### 10.2 Visit 15

**Visit 15** will be conducted either over the telephone or in person at the clinical study site on Study Day 150 ± 5 days. This visit will include:

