#### 13.2.2.1 Primary Effectiveness Endpoints

There are two primary effectiveness endpoints.

- A1C after at least 6 weeks of continuous Phase 2 participation compared to baseline
- A1C at Visit 16, 19, 21, and 23 compared to baseline
- Percentage of time in range (70-180 mg/dL) during Phase 2 and separately during Phase 3 of the hybrid closed-loop phase as compared to Phase 1 (standard therapy)

#### A1C – Phase 2

A1C after at least 6 weeks of continuous Phase 2 participation will be compared to baseline A1C as measured by the core laboratory by calculating the change from baseline in A1C at the appropriate follow-up visit for each subject. Given the nature of this measure, continuous device use is essential for unbiased measurement of A1C. Therefore, the follow-up A1C used in the analysis of this endpoint will include only data from the subjects with at least 6 weeks of continuous Phase 2 participation, either prior to study pause or after recommencement, depending on the length of continuous participation and availability of the A1C measurements. The A1C collected at the latest follow-up visit during Phase 2 will be used, assuming it was collected after at least 6 weeks of subject's participation in Phase 2.

The change in A1C is calculated as A1C at follow-up minus baseline A1C (where negative change indicates decrease or improvement in A1C). The null hypothesis associated with this endpoint states that the mean change in A1C is greater than or equal to zero. Rejection of the null hypothesis indicates that the observed data support the alternative hypothesis that the mean change in A1C is less than zero.

The hypotheses associated with the first primary endpoint are defined as:

$$H_0: \mu \geq 0$$

$$H_1: \mu < 0$$

where  $\mu$  is the mean of the per subject differences in A1C from baseline to follow-up.

#### A1C – Phase 3

A1C at Visit 16 (~6 months total HCL participation) will be compared to baseline A1C as measured by the core laboratory by calculating the change from baseline in A1C at follow-up visit for each subject.

The change in A1C is calculated as A1C at follow-up minus baseline A1C. There are no hypotheses associated with this endpoint.

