### **Percentage of Time in Range 70-180 mg/dL – Phase 3**

The percentage of time in range 70-180 mg/dL during Phase 3 of the hybrid closed-loop phase will be compared to standard therapy by calculating the change between the time in range percentages between Phase 3 of hybrid closed-loop and Phase 1 (standard therapy) for each subject. The change in percentage of time in range 70-180 mg/dL is calculated as the percentage of time in range during Phase 3 minus the percentage of time in range during Phase 1. There are no hypotheses associated with this endpoint.

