## 13.4 Analysis Sets

The following analysis sets are planned for the study and will apply to the endpoints through the end of Phase 2. There are no prespecified analysis sets for Phase 3; all available data will be used to summarize Phase 3 endpoints:

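### Phase 3 A1C and time in range are summarised only in subjects who chose to continue, with no comparison to those who stopped, and the prevailing SAP ends its A1C analyses at Visit 19.

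*Protocol*

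**What the plan says.** **Endpoints.** Protocol Section 13.2.2.1 lists "A1C at Visit 16, 19, 21, and 23 compared to baseline" among the primary effectiveness endpoints, together with Phase 3 time in range. The Phase 3 A1C paragraph that follows reads "A1C at Visit 16 (~6 months total HCL participation) will be compared to baseline A1C as measured by the core laboratory" and then adds: "There are no hypotheses associated with this endpoint". Phase 3 time in range is "calculated as the percentage of time in range during Phase 3 minus the percentage of time in range during Phase 1", also without a hypothesis.

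**Who is analysed.** Protocol Section 13.4 and SAP Section 7.1 set no analysis set for Phase 3; "all available data will be used to summarize Phase 3 endpoints". Protocol Section 13.10 and SAP Section 7.5 rule out imputation.

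**Who is still there.** Under Protocol Section 10 a subject may leave at Visit 13. The reason is documented, but "This will not be considered an early withdrawal from the study". Consent is taken separately for each half of the extension: by Visit 13 for the first, and "consent for second 6-months of Phase 3 must occur on or before Visit 19".

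**The SAP.** It takes precedence over the protocol (SAP Section 1; Protocol Section 13.11). Section 2.3 gives Phase 3 as 6 months, where the protocol gives 12. Sections 6.6 and 7.6 take Visit 19 as the end of Phase 3. Sections 3.2 and 4 name only Phase 2 primary endpoints, and Sections 3.3 and 6 list A1C at Visits 13, 16 and 19 as secondary. On Phase 3 glucose metrics the SAP is not consistent with itself: Section 3.3 includes them, but the restated list in Section 6 covers Phase 2 only.

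**The concern.** The study is single-arm and open. Subjects see their own glucose data and clinicians review device data with them, so each decision to continue is made with knowledge of how well the system has worked for that person. With no control arm, nothing offsets a change in who remains.

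Each Phase 3 summary is a within-subject change, so every contributor keeps a matched baseline. The set of contributors can still differ between Phase 2, the first half of Phase 3 and the second half. A reader who sets the results for Visits 13, 16, 19, 21 and 23 side by side will read a trend over time, and part of that trend may be a change of sample. Neither document plans anything that would let the reader tell the two apart.

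The second problem is one of specification. Taken at its word, the prevailing document stops at Visit 19, so the second half of the protocol's extension has no planned by-visit A1C analysis. What is at stake is the long-term effectiveness description, which the sponsor intends to submit separately from the Phase 2 results.

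**Working it through.** **1. The plan's own figures.** No Phase 3 figure is stated. The Phase 2 sample sizes supply the only effect sizes available: A1C change -0.5% with SD 0.8%, and time in range +10 points with SD 15 points, both at one-sided 1.25% and 90% power (Protocol Sections 13.3.1 and 13.3.2). The normal approximation n = ((z for 0.9875 + z for 0.90) × SD/difference)² gives ((2.241 + 1.282) × 1.6)² = 31.8, so 32, for A1C, and ((2.241 + 1.282) × 1.5)² = 27.9, so 28, for time in range. The exact paired t-test (noncentral t) gives 35 and 31, which match the plan.

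**2. Choices and analysis text behind each A1C visit.**

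| Visit (day) | Choices to continue | Protocol primary section | Protocol secondary (13.2.4) | SAP secondary (3.3, 6) |
|---|---|---|---|---|
| 16 (180) | one | listed, named in analysis text | yes | yes |
| 19 (270) | one | listed only | no | yes, as end of Phase 3 |
| 21 (360) | two | listed only | no | no |
| 23 (450) | two | listed only | yes, as end of Phase 3 | no |

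Visit 19 can be completed on the first consent. The second consent bears on Visits 21 and 23 and on CGM data after Visit 19.

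**3. Illustration A: two groups.** Let c be the proportion continuing. The documents give no value, so c is assumed. Difference between the reported and the all-subject mean = (1 - c) × (stayer mean - leaver mean). Take stayers at -0.50% A1C and +10 points time in range, and leavers at no change.

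| c | All-subject A1C change | A1C difference | All-subject time in range | Time-in-range difference |
|---|---|---|---|---|
| 0.90 | -0.45% | 0.10 × 0.50 = 0.05 | 9 points | 1 point |
| 0.80 | -0.40% | 0.20 × 0.50 = 0.10 | 8 points | 2 points |
| 0.70 | -0.35% | 0.30 × 0.50 = 0.15 | 7 points | 3 points |

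If leavers had half the benefit (-0.25%), the A1C difference at c = 0.80 falls to 0.20 × 0.25 = 0.05. If leavers equal stayers it is zero. If leavers did better than -0.50%, the sign changes.

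With two choices at 90% each, retention after the second is 0.90 × 0.90 = 0.81. The difference is then 0.05 at Visits 16 and 19, and 0.19 × 0.50 = 0.095 at Visits 21 and 23. A step of this kind between Visit 19 and Visit 21 would come from composition alone.

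**4. Illustration B: graded selection.** Let benefit and the tendency to continue have correlation ρ, with a true all-subject mean of -0.50% and SD 0.8%. Expected change in continuers = -0.50 - ρ × 0.8 × φ(z)/c, where z is the normal quantile of c. At c = 0.80, z = 0.842 and φ(z)/c = 0.280/0.80 = 0.350.

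- ρ = 0: -0.50%, no bias.
- ρ = 0.2: -0.50 - 0.2 × 0.8 × 0.350 = -0.556%.
- ρ = 0.6: -0.50 - 0.6 × 0.8 × 0.350 = -0.668%.
- ρ = -0.2: -0.50 + 0.056 = -0.444%, so benefit is understated.

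For ρ from 0.2 to 0.6 the range is -0.531% to -0.594% at c = 0.90 and -0.579% to -0.738% at c = 0.70. Time in range at c = 0.80 becomes 10 + ρ × 15 × 0.350, that is 11.05 to 13.15 points against a true 10.

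**The case against.** The strongest reply is that Phase 3 is descriptive. It carries no hypothesis (Protocol Sections 13.2.2.1 and 13.5), and success rests on Phase 2 rates of severe hypoglycaemia and ketoacidosis (Protocol Section 13.3, SAP Section 2.5). The effect among people who go on using the system is a legitimate thing to describe. A subject who exits at Visit 13 returns the devices, so a Phase 3 change for the whole cohort is hypothetical. The plan also collects what a careful reader would want: the reason for exit at Visit 13, an A1C at Visit 13, and an A1C at Phase 3 early withdrawal (Protocol Sections 10, 9.9 and 10.11). All of this stands. It limits the point to interpretation and makes a mixed model a sensitivity analysis, not a replacement.

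Three stronger readings are tempting, and the documents do not support them.

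- A reader might infer that the long-term benefit will be overstated. No retention figure or outcome for leavers is given, and the direction depends on who stops.
- A reader might infer that every Phase 3 result depends on two decisions to continue. Visits 16 and 19 depend on one.
- A reader might infer that Visit 16 is the only Phase 3 visit with an A1C analysis. That is true only of the analysis text in the primary section. Visit 23 is a protocol secondary time point and Visit 19 a SAP secondary one. Only Visit 21 is listed nowhere beyond the primary bullet. The exploratory item on A1C at the last follow-up visit is not an analysis by visit and does not say whether it reaches into Phase 3.

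The reply does not meet the central gap: no planned output separates persistence of effect from a change in who contributes.

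**Conclusion.** The point holds as a limit on what Phase 3 can show, and as a conflict between the two documents. As planned, Phase 2 and Phase 3 results for A1C and time in range come from different, self-selected groups, and nothing tabulated would show how far the groups differ.

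The size is unknown. With assumed retention of 90% to 70%, stayers at the design effect and leavers at no change, the difference is about 0.05 to 0.15 A1C points and 1 to 3 points of time in range. Leavers with no change at all is a severe assumption, and half the benefit halves those figures. The bias is zero if continuing is unrelated to benefit and reverses if those who benefit more stop.

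The specification gap needs no assumption. The protocol makes four Phase 3 A1C visits primary and explains one. The SAP overrides it with a shorter Phase 3, no Phase 3 primary endpoint and no by-visit A1C analysis after Visit 19. Phase 2 error control, Phase 2 power and the success criterion are untouched.

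**What to change.** 1. **Align the documents.** Amend the SAP (Sections 2.3, 3.2, 3.3, 4, 6, 6.6 and 7.6) to the protocol's 12-month Phase 3 with Visit 23 as its end. In both documents, state that change from baseline in A1C is reported at Visits 16, 19, 21 and 23, with the number contributing at each visit and the reasons for not continuing.
2. **Show who stayed.** For A1C and time in range, tabulate baseline and Phase 2 change for subjects who did and did not enter each 6-month interval. Then show Phase 2 and Phase 3 change in the same continuing subjects. If the second table shows the effect held within subjects, durability can be described without the selection question.
3. **Sensitivity analysis only.** Fit a repeated-measures mixed model of A1C change in mITT subjects, with baseline A1C and visit as terms. Use as the Phase 2 value the A1C chosen by the pause rule (Protocol Section 13.1, SAP Section 2.8), so that the model agrees with the Phase 2 primary analysis. State that it assumes data are missing at random given the observed values.

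The cost is SAP wording, two tables and one model. No new visits, samples or subjects are needed. The drawback for the sponsor is a little more analysis and a long-term effect that may look less favourable.

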### **Percentage of Time in Range 70-180 mg/dL – Phase 2**

The percentage of time in range 70-180 mg/dL during Phase 2 of the hybrid closed-loop phase will be compared to standard therapy by calculating the change between the time in range percentages between Phase 2 of hybrid closed-loop and Phase 1 (standard therapy) for each subject. The change in percentage of time in range 70-180 mg/dL is calculated as the percentage of time in range during Phase 2 minus the percentage of time in range during Phase 1 (where positive change indicates increased time in range). The null hypothesis associated with this endpoint states that the mean change in percentage of time in range 70-180 mg/dL is less than or equal to zero. Rejection of the null hypothesis indicates that the observed data support the alternative hypothesis that the mean change in percentage of time in range 70-180 mg/dL is greater than zero.

The hypotheses associated with this primary endpoint are defined as:

$$H_0: \mu \leq 0$$

$$H_1: \mu > 0$$

where  $\mu$  is the mean of the per subject differences in percentage of time in range 70-180 mg/dL during Phase 2 of hybrid closed-loop phase compared to Phase 1.

### **Percentage of Time in Range 70-180 mg/dL – Phase 3**

The percentage of time in range 70-180 mg/dL during Phase 3 of the hybrid closed-loop phase will be compared to standard therapy by calculating the change between the time in range percentages between Phase 3 of hybrid closed-loop and Phase 1 (standard therapy) for each subject. The change in percentage of time in range 70-180 mg/dL is calculated as the percentage of time in range during Phase 3 minus the percentage of time in range during Phase 1. There are no hypotheses associated with this endpoint.

#### **13.2.3 Secondary Objective**

The secondary objective of the study is to evaluate additional glycemic measures of effectiveness of the Omnipod Horizon™ System.

#### **13.2.4 Secondary Endpoints**

The secondary objective will be evaluated using the following per subject endpoints *with* prespecified hypotheses:

- Glucose metrics from system CGM during the hybrid closed-loop phase for Phase 2 will be compared to Phase 1 overall:
  - % of time > 180 mg/dL
  - % of time < 70 mg/dL

Additional per subject secondary endpoints *without* prespecified hypotheses used to evaluate the secondary objective include:

- A1C:

- A1C after at least 8 weeks of continuous Phase 2 participation at the end of Phase 2 (Visit 13), at 6 months (Visit 16), and at the end of Phase 3 (Visit 23; approximately 15 months)
  - Change from baseline in A1C after at least 6 weeks of continuous Phase 2 participation, after at least 8 weeks of continuous Phase 2 participation at the end of Phase 2 (Visit 13), at 6 months (Visit 16), and at the end of Phase 3 (Visit 23; approximately 15 months)
  - Proportion of subjects demonstrating an improvement from baseline in A1C after at least 6 weeks of continuous Phase 2 participation, after at least 8 weeks of continuous Phase 2 participation at the end of Phase 2 (Visit 13), at 6 months (Visit 16), and at the end of Phase 3 (Visit 23; approximately 15 months)
- Glucose metrics from system CGM during the hybrid closed-loop phase during Phase 2, and separately during Phase 3 will be compared to Phase 1 during the day, overnight, and overall:
  - Mean glucose
  - % of time in range 70-180 mg/dL
  - % of time in range 70-140 mg/dL
  - % of time > 180 mg/dL
  - % of time  $\geq$  250 mg/dL
  - % of time  $\geq$  300 mg/dL
  - % of time < 70 mg/dL
  - % of time < 54 mg/dL
  - Standard deviation
  - Coefficient of variation
- Percentage of time in hybrid closed-loop as proportion of overall device usage time during Phase 2, and separately during Phase 3
- Glucose management indicator (GMI) based on overall mean glucose during Phase 2, and separately during Phase 3 will be compared to Phase 1
- Insulin requirements during Phase 2, and separately during Phase 3 will be compared to Phase 1:
  - Total daily insulin (TDI) (units, units/kg)
  - Total daily basal insulin (units, units/kg)
  - Total daily bolus insulin (units, units/kg)
- Change from baseline in BMI ( $\text{kg}/\text{m}^2$ ) at end of Phase 2, and at end of Phase 3

### **Percentage of Time in Range >180 mg/dL**

The percentage of time in range >180 mg/dL during Phase 2 of hybrid closed-loop phase will be compared to standard therapy (Phase 1) by calculating the change between the time in range percentages between Phase 2 and Phase 1 for each subject. The change in percentage of time in range >180 mg/dL is calculated as

the percentage of time in range during Phase 2 minus the percentage of time in range during Phase 1. The null hypothesis associated with this endpoint states that the mean change in percentage of time in range  $>180$  mg/dL is greater than or equal to zero. Rejection of the null hypothesis indicates that the observed data support the alternative hypothesis that the mean change in percentage of time in range  $>180$  mg/dL is less than zero.

The hypotheses associated with this secondary effectiveness endpoint are defined as:

$$H_0: \mu \geq 0$$

$$H_1: \mu < 0$$

where  $\mu$  is the mean of the per subject differences in percentage of time in range  $>180$  mg/dL during Phase 2 of hybrid closed-loop compared to the standard therapy phase (Phase 1).

#### **Percentage of Time in Range $<70$ mg/dL**

The percentage of time in range  $<70$  mg/dL during Phase 2 of hybrid closed-loop phase will be compared to standard therapy (Phase 1) by calculating the change between the time in range percentages between Phase 2 and Phase 1 for each subject. The change in percentage of time in range  $<70$  mg/dL is calculated as the percentage of time in range during Phase 2 minus the percentage of time in range during Phase 1. The null hypothesis associated with this endpoint states that the mean change in percentage of time in range  $<70$  mg/dL is greater than or equal to zero. Rejection of the null hypothesis indicates that the observed data support the alternative hypothesis that the mean change in percentage of time in range  $<70$  mg/dL is less than zero.

The hypotheses associated with this secondary effectiveness endpoint are defined as:

$$H_0: \mu \geq 0$$

$$H_1: \mu < 0$$

where  $\mu$  is the mean of the per subject differences in percentage of time in range  $<70$  mg/dL during Phase 2 of hybrid closed-loop compared to the standard therapy phase (Phase 1).

